### **3.6.8        Pharmacokinetic Set B**

The Pharmacokinetic Set B (PKSB) will consist of all subjects from the SSB who provide at least 1 PK sample during Part B.

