- TE ADAb status negative is defined as having no samples either ADAb positive or with values  $\geq$ MSR -fold increase from baseline.

Once determined positive, the highest titer during Part A and Part B (including Escape and SFU) is used to categorize the subject.

- Positive  $<512$ ,
- Positive  $512- \leq 1024$ ,
- Positive  $>1024$ .

In addition, for some outputs also the subjects with TE ADAb status negative will be presented.

The TE ADAb will be also defined for the different treatment periods. For each Period the SFU visit will be considered:

- Part A TE ADAb status positive is defined as either (i) baseline ADAb negative subjects having at least one ADAb confirmed positive sample post baseline during Part A or ii) baseline ADAb positive subjects with at least one post baseline sample with  $\geq$ MSR increase from baseline on CZP treatment during Part A. Once determined positive, the highest titer during Part A is used to categorize the subject.
- Part A TE ADAb status negative is defined as having no samples either ADAb positive or with values  $\geq$ MSR increase from baseline during Part A.
- Part B TE ADAb Status positive is defined as either (i) baseline ADAb negative subjects having at least one ADAb confirmed positive sample post baseline during Part B or ii) baseline ADAb positive subjects with at least one post baseline sample with  $\geq$ MSR increase from baseline on CZP treatment during Part B. Once determined positive, only the highest titer during Part is used to categorize the subject. For subjects with flare in Part B, any assessments after Escape treatment are not included.
- Part B TE ADAb Status negative is defined as having no samples either ADAb positive or with values  $\geq$ MSR increase from baseline during Part B (excluding any values up to 8 weeks post first Part B dose).
- Escape TE ADAb Status positive is defined as either (i) baseline ADAb negative subjects having at least one ADAb confirmed positive sample post baseline during Escape Part or ii) baseline ADAb positive subjects with at least one post baseline sample with  $\geq$ MSR increase from baseline on CZP treatment during Escape Part B. Once determined positive, only the highest titer during Escape is used to categorize the subject.

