- Escape TE ADAb Status negative is defined as having no samples either ADAb positive or with values  $\geq$ MSR increase from baseline during Escape Part. Once determined positive, only the highest titer during Escape is used to categorize the subject.

Summaries will be done using PKSB.

Summary of shift from Baseline ADAb status with titer classification to TE ADAb Status with titer classification by treatment group and for all subjects will be presented during the entire study.

The shift table will be repeated for

- Part A TE ADAb status with titer classification to Part B TE ADAb status with titer classification by treatment group and for all subjects during Part B.
- Part B TE ADAb status with Part B titer classification to Escape Part TE ADAb status with Escape titer classification by treatment group and for all subjects during Escape Part.

The time to achieving TE ADAb for all subjects will be analyzed based on Kaplan-Meier methods. Subjects will be considered to have an event at the time where treatment-emergent ADAb positive is first achieved during treatment period excluding Baseline/pre-treatment. Subjects classified as treatment-emergent ADAb negative will be censored at the time of last available ADAb result. The median and 95% CI based on the Kaplan-Meier estimation will also be presented. A plot of time to first ADAb positivity will be presented.

Number and percentage of subjects with ADAb titer above the specified cut point (“categorized”) at any visit during the treatment period, separated by treatment group will be presented.

A summary of flare responder during Part B (NRI) and ASDAS MI responder at Week 96 (NRI) by treatment group and by highest ADAb titer (“categorized”) per subject will be presented during Part A and Part B (excluding Escape). This table will be repeated for Part B (excluding Escape).

A scatter plot of CZP Plasma Concentration and ADAb titer during Part A for all subjects will be presented. The scatter plot will be repeated for Part B by treatment group.

Spaghetti plots of ADAb titer on a loglog scale by week from CZP first dosing separated by treatment group and TE ADAb status/titer classification will be presented for subjects with flare and no flare per NRI approach.

All individual ADAb results will be listed at subject level.

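### SAP Section 9.2 allows Part B ADAb negative status with no evaluable sample, and its 8-week window, written into one rule only, lets the positive and negative classes overlap

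*SAP*

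**What the plan says.** Section 9.2 sets treatment-emergent (TE) ADAb status separately for Part A, Part B and Escape.

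- **Part B negative:** "Part B TE ADAb Status negative is defined as having no samples either ADAb positive or with values" at or above the MSR increase from baseline during Part B, with the qualifier "excluding any values up to 8 weeks post first Part B dose".
- **Part B positive:** the first route is "baseline ADAb negative subjects having at least one ADAb confirmed positive sample post baseline during Part B". The second is an MSR increase in baseline-positive subjects. Neither route carries the 8-week qualifier.
- **Escape cut-off:** the Part B positive bullet adds "For subjects with flare in Part B, any assessments after Escape treatment are not included".
- **Follow-up:** the safety follow-up (SFU) visit is considered for each period.

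These summaries use the Pharmacokinetic Set B, which Section 3.6.8 defines as "all subjects from the SSB who provide at least 1 PK sample during Part B". Entry depends on a PK sample, not on an ADAb result.

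Part B status feeds two shift tables in Section 9.2. One is "Part A TE ADAb status with titer classification to Part B TE ADAb status with titer classification by treatment group". The other runs from Part B status to Escape status. A separate table shows flare by highest categorized titer and is repeated for Part B alone.

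**The concern.** A class defined only by the absence of a finding also takes in people in whom nothing was looked for. Here two exclusions can remove every usable value: the 8-week window at the start of Part B and the cut-off at escape. A subject who flares early and escapes before the window closes is left with nothing to evaluate and still satisfies the negative rule.

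Those subjects are not a random subset. Each one is a flare in the primary analysis, and at the planned rates they fall mostly in the placebo arm. In the Part A to Part B table, a Part A positive subject can appear to have become negative with no evaluable Part B value behind it. In the Part B to Escape table, the same subject, if positive on re-treatment, can appear as a new conversion.

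Because the window sits in one rule only, the two classes are also not mutually exclusive, and no sentence says which prevails.

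**Working it through.** **Can such subjects exist?** Under Section 3.2.22 a single ASDAS above 3.5 at any Part B visit is a flare. The date offsets in Section 3.2.23 imply scheduled ASDAS visits at Weeks 50, 52 and 56: 2 weeks after Week 48 and after Week 50, and 6 weeks from Week 50 to the second missed visit. Section 2.3.3 puts escape 2 weeks after the qualifying assessment, or earlier. Flares at Weeks 50 and 52 therefore lead to escape at about Weeks 52 and 54, before the window closes at 48 + 8 = Week 56.

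**Apply both rules as written** to a baseline-negative subject who escapes inside the window:

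| Part B ADAb samples | Positive rule met | Negative rule met |
|---|---|---|
| none | no | yes |
| only a negative sample in the first 8 weeks | no | yes, although that sample is excluded |
| a confirmed positive sample in the first 8 weeks | yes | yes |

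If the window were added to the positive rule and nothing else changed, all three rows would become negative. Aligning the window is therefore not enough without a requirement for an evaluable sample. The overlap in the third row is not confined to escapees. It arises for any baseline-negative subject whose only confirmed positive Part B sample is early.

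**Does another rule catch them?** The ADAb missing-data rules in Section 9.2 cover a missing titer and a missing confirmatory result, not a missing status. The analysis set does not remove these subjects. An escapee's SFU sample comes after escape treatment and does not count towards Part B.

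**Size.** The SAP states no figure for this, so there is none to reproduce. Inputs are the flare-free rates S in Section 2.4 (45% placebo, 75% half-dose, 80% full-dose) and 70 subjects per arm. The assumption is a constant hazard over the 48 weeks of Part B, so the share flaring by t weeks is 1 − S^(t/48).

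For flares at Weeks 50 or 52, t = 4:
- Placebo: 1 − 0.45^(4/48) = 6.4%, or 4.5 of 70
- Half-dose: 1 − 0.75^(4/48) = 2.4%, or 1.7 of 70
- Full-dose: 1 − 0.80^(4/48) = 1.8%, or 1.3 of 70

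Expected placebo flares are 70 × 0.55 = 38.5, so 4.5 is about 12% of them.

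Placebo range:
- If unscheduled assessments let flares up to Week 54 lead to escape by Week 56, t = 6: 1 − 0.45^(6/48) = 9.5%, or 6.6 of 70.
- If flares come later and the hazard over the first 4 weeks is half the constant value (assumption): 1 − 0.45^(2/48) = 3.3%, or 2.3 of 70.

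**The case against.** The best defence is that the SAP already implies the sensible reading. Section 3.1 calls for a missing category or non-missing denominators, and Section 9.2 bases classification on assay results, so a subject without a usable result should simply be missing. A careful programmer might do that. But neither section says when Part B status is missing, and the definition itself returns negative, so nothing is left missing for Section 3.1 to handle. A subject with an early negative sample does have an assay result; it is the rule that discards it.

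Several limits on the point do stand:

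- A reader might infer that every early escapee who was positive in Part A is recorded as having lost antibodies. The text does not support that. A baseline-negative subject with a confirmed positive sample early in Part B also meets the positive rule, so that status is contradictory rather than plainly negative.
- A reader might infer that nothing was measured. Early samples may well exist, and all individual ADAb results are listed. What is missing is an evaluable value.
- A reader might infer that early flares are placed in the lowest antibody class of the flare-by-titer table. That table uses the highest categorized titer, the listed titer classes are all positive, and negatives are shown only in some outputs. It is exposed only if it shows a negative row derived from Part B status.
- The planned rates count premature withdrawals as flares. Those who withdraw without escaping have an SFU visit that is considered for the period, so they may be evaluable. The figures above are somewhat high on this account.
- The Escape negative rule has no 8-week window and takes the SFU visit into account, so a status without a sample should be rarer there.

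**Conclusion.** The definition is wrong as written. Part B negative status needs no evaluable value, and the unequal window makes the two Part B classes overlap with no tie-break.

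The reach is limited to the descriptive Part A to Part B and Part B to Escape shift tables, plus the Part B flare-by-titer table under the condition given above. The primary test, the entire-study shift table and the time-to-ADAb analysis do not use Part B status and are unaffected. Section 9.2 specifies no test of ADAb between arms, so a claim that such a comparison is biased would go further than the document allows.

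A few subjects per arm are involved, unevenly: about 4.5 of 70 on placebo against 1.7 and 1.3 on half-dose and full-dose. This rests on the planned rates, a constant hazard and escape by Week 56 only after flares at Weeks 50 or 52. The count covers only subjects for whom the rule leaves no value under any sampling schedule. The number of false shifts is smaller, because a false loss of antibodies also requires Part A positivity. The SAP gives no rate for that, so the number cannot be computed. The error is small in numbers but tied to both arm and outcome, and it is worth correcting.

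**What to change.** In Section 9.2:

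1. Apply the 8-week window identically to the Part B positive and negative rules, or to neither, so that no subject can meet both.
2. Define Part B and Escape negative as at least one evaluable sample in the period and none meeting the positive definition. For Part B, evaluable means before the first escape dose and, if the window is kept, after it.
3. Report subjects with no evaluable sample in a separate *not evaluable* row by arm, outside the percentages and the negative cells of the shift tables. Do the same in the flare-by-titer table if it shows a negative row.

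Steps 1 and 2 belong together. With the window left in the negative rule only, a subject with an early confirmed positive could be both positive and not evaluable. The cost is a sentence or two in Section 9.2 and one extra table row, with no new data.

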### **2.3.2 Part B**

**Period 3** (Double-Blind Period): Week 48 to Week 96, PBO-controlled

Subjects must meet the sustained remission criteria in order to be randomized to Part B. These subjects in sustained remission will be randomized in a 1:1:1 ratio to one of the following treatment arms:

- CZP administered at a dose of 200mg Q2W (full-dose)
- CZP administered at a dose of 200mg Q4W (half-dose)
- PBO

All subjects who discontinue prematurely from the study for any reason during the Double-Blind Period will be treated at the discretion of the Investigator.

The final study assessments will be performed at Week 96. Subjects experiencing a flare during the Double-Blind Period will receive escape-treatment as defined in Section [2.3.3](#).

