## 9.2 Immunogenicity

Immunogenicity will be assessed through listing of individual results by subject and summary tables. Immunogenicity data will be correlated with PK and efficacy readout.

A cut point will be determined by the bioanalytical laboratory during assay validation. This cut point will be used to determine the status of ADAb in the test sample.

The following definitions will be applied regarding classification of test samples:

- An ADAb status will be confirmed as positive for any sample with an ADAb level that is positive screen and positive immunodepletion.
- An ADAb status of negative will be concluded for any sample with an ADAb level that is either negative screen or positive screen and negative immunodepletion.

Confirmed positive samples will be titrated. The dilution factor will be reported. The titer represents the last dilution factor of the sample's titration series still scoring positive in the screening ADAb assay. ADAb titer dilution factor is presented in the listings and summaries excluding the minimum required dilution, i.e. reportable values are divided by 100.

If the titer for an ADAb level that is positive screen and positive immunodepletion is missing, then a conservative will be used and ADAb status will be consider as positive. No imputation rules apply for the missing titer.

If the ADAb level is positive screen but no confirmatory result could be determined, then then a conservative will be used and ADAb status will be consider as positive.

Anomalous value will be not included in summaries/analysis and will be reviewed and flagged by pharmacokineticist.

Subjects will have the following Baseline ADAb status:

Baseline ADAb Status positive is defined as having an ADAb confirmed positive inhibition result at baseline, Baseline ADAb Status negative is defined as having negative inhibition result at baseline.

Subjects will receive a treatment-emergent ADAb status, inclusive of Baseline and Post-Baseline results (including SFU), and be classified as follows based on the ADAb assay results:

- TE ADAb status positive is defined as either (i) baseline ADAb negative subjects having at least one ADAb confirmed positive sample post baseline or ii) baseline ADAb positive subjects with at least one post baseline sample with  $\geq$ minimum significant ratio (MSR) -fold

increase from baseline on CZP treatment. The MSR will be defined during the process of sample analysis and is disease-specific.

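### The time-to-ADAb Kaplan-Meier analysis is planned only for all arms pooled, so after Week 48 it cannot be attributed to any one regimen

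*SAP*

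**What the plan says.** Section 9.2 of the SAP plans one time-to-onset analysis for antibodies: "The time to achieving TE ADAb for all subjects will be analyzed based on Kaplan-Meier methods". The median with its 95% CI and a plot are to accompany it. No split by treatment group is given, and nothing in the section ends or divides the curve at Week 48 or at escape.

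The population is set in the same section: "Summaries will be done using PKSB". Section 3.6.8 says that PKSB "will consist of all subjects from the SSB who provide at least 1 PK sample during Part B", so it covers every arm. Section 2.3.2 gives the allocation: "These subjects in sustained remission will be randomized in a 1:1:1 ratio to one of the following treatment arms".

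The event rule is: "Subjects will be considered to have an event at the time where treatment-emergent ADAb positive is first achieved during treatment period excluding Baseline/pre-treatment". The censoring rule is: "Subjects classified as treatment-emergent ADAb negative will be censored at the time of last available ADAb result". The status that these rules use is wider in scope: "Subjects will receive a treatment-emergent ADAb status, inclusive of Baseline and Post-Baseline results (including SFU").

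The main shift table in the same section is planned both ways, "to TE ADAb Status with titer classification by treatment group and for all subjects will be presented during the entire study".

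**The concern.** A Kaplan-Meier curve is read as the onset pattern under some exposure. Here exposure is uniform until Week 48 and then splits three ways by randomization. Subjects on placebo or half dose who flare later move to full dose, the placebo subjects with loading doses. One pooled curve across that boundary turns from the profile of a regimen into an average over a changing mixture.

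The SAP names the evolution of immunogenicity as an objective (Section 2.1.4). It describes the study as evaluating immunogenicity, among other things, under continued, reduced and withdrawn treatment (Section 2.3). Whether the timing of antibody onset differs between those arms is a natural question of this design, and the pooled curve cannot show it.

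A second, smaller matter is that the event rule refers to the treatment period while TE status also uses SFU samples. It is then unclear what time to give a subject whose first positive sample is the SFU sample.

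**Working it through.** The SAP states no antibody rate and no expected median, so there is no planned figure to reproduce. The check sets the definitions side by side and adds arithmetic on stated design figures and labelled assumptions.

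**1. Exposure under the curve.**
- Week 0 to 48: all subjects receive the same Part A regimen (Section 3.7). The pooled curve is interpretable here, for subjects selected by later randomization.
- From Week 48: 1:1:1 allocation, planned at 70 per arm (Section 2.4), so 70/210 = 33% are on full dose, 33% on half dose and 33% on placebo.
- By Week 96: Section 2.4 assumes 75% without flare on half dose and 45% on placebo, so 25% and 55% flare. If all of them escaped, the number on full dose would be 70 + 0.25 × 70 + 0.55 × 70 = 70 + 17.5 + 38.5 = 126, and 126/210 = 60%. This is an upper bound, because the primary flare definition also counts withdrawals.

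The full-dose share under one curve thus goes from 100% to 33% and then towards at most 60%.

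**2. Neighbouring outputs in Section 9.2.**
- The shift tables are by treatment group and overall.
- The table of titers above the cut point is by treatment group.
- The scatter plot of concentration against titer is for all subjects in Part A and is repeated by treatment group in Part B.
- Part B TE ADAb positive status leaves out assessments after escape treatment, and the Escape Part has its own status.

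The plan already handles the Week 48 and escape boundaries elsewhere. The Kaplan-Meier analysis is the exception. The shift tables say whether a subject converted, not when. The spaghetti plots of titer by week are split by arm but give no estimate.

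**3. What pooling could hide (assumptions only).** Take 30% TE positive by Week 48, then hazards h per 4 weeks over 12 intervals, with no escape effect. Cumulative positivity at Week 96 is 1 − 0.70 × (1 − h)^12.
- Full dose, h = 0.02: 45.1%
- Half dose, h = 0.04: 57.1%
- Placebo, h = 0.005: 34.1%
- Pooled: (45.1 + 57.1 + 34.1)/3 = 45.4%

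The spread is 57.1 − 34.1 = 23 points. In this example the half-dose arm reaches its median before Week 96 and the pooled curve does not. The spread only restates the chosen hazards; with equal hazards it is zero. The placebo figure also ignores re-exposure after flare.

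**4. First positive at the SFU visit.**
- Section 3.3.2 ends the treatment period at Week 96 for Part B completers, and the SFU visit comes 10 weeks after the last dose (Section 2.3.2). Read this way, a subject first positive at SFU is TE positive, so falls outside the censoring rule, and has no on-treatment event. TE-negative subjects censored at an SFU sample would also stay at risk over time in which no event can count.
- Section 9.2 also says that the SFU visit counts towards each period's status, and Section 9.1 uses a treatment period that takes in SFU for the individual plots. Read this way, the subject has an event at the SFU date.

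To size the choice, assume 210 subjects, 63 (30%) positive on treatment, and 4, 10 or 21 (about 2%, 5%, 10%) first positive at SFU. Crude incidence is:
- counted as events: 67/210 = 31.9%, 73/210 = 34.8%, 84/210 = 40.0%
- censored: 63/210 = 30.0% in each case
- dropped: 63/206 = 30.6%, 63/200 = 31.5%, 63/189 = 33.3%

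The rule chosen moves the result by about 2 to 10 points over this range.

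**The case against.** The other side has four good arguments.

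First, this is one descriptive figure without a hypothesis test. The stated objective is to follow immunogenicity and does not ask for a comparison between arms. Shift tables by arm, including Part A to Part B and Part B to Escape, already cover reduction, withdrawal and re-exposure. This stands as to status and lowers the weight of the point. It does not supply timing, and this is the only planned time-to-onset estimate.

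Second, a reader might infer that the curve describes no regimen at all. The documents do not support that, since every subject is on the same regimen up to Week 48.

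Third, a reader might infer that subjects first positive at SFU have neither an event nor a censoring time, so that the analysis cannot be computed for everyone. That requires bringing the end date of Section 3.3.2 into Section 9.2. The wording of Sections 9.1 and 9.2 supports dating the event at SFU, and where the SAP wants SFU left out, as in the laboratory derivations of Section 10.3, it says so. What remains is an unresolved wording, not an impossibility.

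Fourth, censoring at escape may be informative, because escape follows flare and antibody formation may be related to flare. This stands and has to be part of the remedy.

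**Conclusion.** The point holds in a limited form. After Week 48 the pooled curve, and any median reached there, mixes full-dose, half-dose, placebo and escape exposure and cannot be attributed to a regimen. Up to Week 48 it is sound for the Part A regimen among subjects later randomized. The finding rests on the definitions in Sections 2.3.2, 3.6.8 and 9.2 and needs no assumption about rates.

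Its size is not known from the SAP. The 23-point spread is an illustration under assumed hazards, not an estimate. The SFU wording is a secondary clarification, worth roughly 2 to 10 points of crude incidence under the assumed range. The analysis is descriptive and leaves the primary endpoint untouched. It should still be settled before unblinding, so that neither the display nor the handling is chosen with the data in view.

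**What to change.** In Section 9.2:

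- Present the pooled Kaplan-Meier curve to Week 48 only.
- From Week 48, present time to first TE ADAb by randomized arm among subjects not yet TE positive at Week 48, with time counted from Week 48. That subset is defined before randomized treatment starts, so the arms remain comparable.
- Censor the by-arm curves at the first escape injection. Because that censoring may be informative, show a version without it alongside, and report conversions after escape in the existing Escape shift table.
- State whether the exclusion of values up to 8 weeks after the first Part B dose, which Section 9.2 attaches to Part B TE-negative status, applies to these curves.
- State whether a subject first positive at SFU has an event at SFU or is censored at the last on-treatment sample, and apply the same cut-off to TE-negative subjects.

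The cost is a few sentences and one further figure in two versions. No new samples or assays are needed. The risk sets by arm will be smaller than the pooled one, so the later parts of the curves will be less precise.
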